6.1.4.4 Definition of critical structures

Note: All structures must be named for digital RT data submission as listed in the table below. The structures marked as “Required” in the table must be contoured and submitted with the treatment plan. Structures marked as “Required when applicable” must be contoured and submitted when applicable.

Resubmission of data may be required if labeling of structures does not conform to the standard DICOM name listed. Capital letters, spacing, and use of underscores must be applied exactly as indicated.

Standard Name	Description	Validation Required/Required when applicable/Optional
Bladder	Bladder	Required
Femur_R	Right femur	Required
Femur_L	Left femur	Required
Bowel_Small	Small Bowel	Required

Notes from RTOG Anorectal Atlas for contouring of normal structures:

Small Bowel:

The small and large bowel are important structures to consider when planning treatment. To avoid unnecessary time spent contouring the entire abdominal contents, they only need to be contoured up to ~ 1 cm above the PTV. This, in turn, implies that absolute volume of bowel (in cc) is more important than relative volume (in %). Otherwise cases with good exclusion of small bowel from the pelvis (e.g., with a belly board) will be unfairly penalized.

Femoral Heads:

The femoral head and neck should be avoidance structures. Only the femoral heads, not the neck should be drawn.

Large bowel constraint:

There is no large bowel constraint. However, “uninvolved colon” defined as part of the large bowel that lies outside of the CTVs (rectum and part of the rectosigmoid) should be contoured separately from the rectum.

6.1.4.5 Dose Prescription

Target Standard Name	Dose (Gy)	Fraction Size (Gy)	# of fractions	Dose specification technique
PTV 4500	45	1.8	25	Covering 95% of PTV
PTV 5040	50.4	1.8	3	Covering 95% of PTV

6.1.4.6 Planning technique

A 3D conformal radiotherapy planning technique must be used. If not using IMRT, field edges, and MLC blocking must be conformal to the PTVs. The dose distributions must include corrections for tissue density heterogeneities. Regardless of planning technique, the dose prescription criteria specified in Section 6.1.4.7 on compliance criteria must be used.

3-D treatment planning guidelines for rectal cancer for this protocol are detailed in:
http://econtour.org/training/rectal_cancer_module.pdf

6.1.4.7 Compliance criteria

The compliance criteria listed here will be used to score each case. Given the limitations inherent in the treatment planning process, the numbers given in this section can be different than the prescription table. The Per Protocol and Variation Acceptable categories are both considered to be acceptable. The Per Protocol cases can be viewed as ideal plans, and the Variation Acceptable category can include more challenging plans that do not fall at or near the ideal results. A final category, called Deviation Unacceptable, results when cases do not meet the requirements for either Per Protocol or Variation Acceptable. Plans falling in this category are considered to be suboptimal and additional treatment planning optimization is recommended.

VxGy (cc), VxGy (%), Vx%(cc), Vx%(%): Volume (cc or %) receiving Dose (Gy, or %)

Dvcc(Gy), Dvcc(%), Dv%(Gy), Dv%(%): Dose (Gy or %) to Volume (cc or % of total volume)

Dmin(Gy) or Dmin(%): Minimum dose is defined to a volume that is the total volume minus 0.03 cc

Dmax(Gy) or Dmax(%): Maximum dose is defined to a volume of 0.03 cc

Dmean(Gy) or Dmean(%): Mean dose in Gy or %

For Normalization purposes two treatment plans are generated, one for each phase of treatment (initial 45 Gy, and subsequent boost volume to 50.4 Gy), each plan normalized to a PTV covering isodose volume of 95% as described in the prescription section (Section 6.1.4.5), V95% = 100%. A combination (plan sum) is required to evaluate the dosimetric compliance criteria for critical structures.

Heterogeneities will be taken into account in the radiation dose calculation, in accordance with the guidelines provided on the IROC website: <http://rpc.mdanderson.org/RPC/home.htm>.

Note: Deviation Unacceptable occurs when dose limits for Variation Acceptable are not

met.

6.1.4.8 Target Volume Constraints and Compliance Criteria

Name of Structure	Dosimetric parameter*	Per Protocol	Variation Acceptable
PTV_4500	D95% (%)	≥95	≥90
PTV_5040	D95% (%) D10(%) (%)	≥95 ≤110	≥90 ≤120

*Note: Percentiles are normalized to prescription doses of 45 Gy and 50.4 Gy respectively.

Name of Structure	Dosimetric parameter	Per Protocol	Variation Acceptable
Bowel_Small	D150cc(Gy)	≤15	≤16.5
	D120cc(Gy)	≤35	≤38.5
	D70cc(Gy)	≤40	≤44
	D35cc(Gy)	≤45	≤49.5
	Dmax(Gy)	≤50	≤55
Femur_L&Femur_R	D50%(Gy)	≤30	≤33
	D40%(Gy)	≤40	≤44
	D5%(Gy)	≤45	≤49.5
	Dmax(Gy)	≤50	≤55
Bladder	Dmean(Gy)	≤40	≤44
E-PTVs	D1cc(Gy)	≤49.5	≤54.5

E-PTVs include any non-PTV tissues.

Note: Constraints related to bowel and bladder are recommendations. Constraints will be scored but any Unacceptable Deviations will not affect the overall plan score. However, all femoral head constraints and the D0.03cc (Gy) for the Bowel_Small will be scored an Unacceptable Deviation if parameters are not met and will be counted in overall plan score.

6.1.4.9 Patient specific QA

Any patient-specific QA that needs to be acquired should follow institutional guidelines. Only sites credentialed for NRG-GI002 can administer pelvic radiation therapy to patients enrolled in this trial. For photon IMRT plans, patient specific QA is highly recommended. QA is performed by delivering the plan onto a phantom and measuring the dose using an ion chamber array or other 2D/3D device. Typically, measured dose distributions will be compared to planned dose distribution using a Gamma criterion of 4% dose difference and 3 mm distance to agreement. The pass rate should be at least 90% measured for the entire plan.

6.1.4.10 Daily Treatment Localization/IGRT

Daily IGRT localization is required for patients treated with IMRT. Either a daily orthogonal kV pair, or CBCT (or MVCT) is acceptable. The boost plan should be imaged with daily CBCT. Institutional guidelines should be followed for daily treatment localization and IGRT. For patients not treated with IMRT, patients should be imaged with an Orthogonal kV (2D) image pair or CBCT (or equivalent) prior to the first fraction, and weekly henceforth. IGRT credentialing is not required for this protocol.

Management of Radiation Dose to the Patient from IGRT

Due to concern about the estimated doses given from IGRT, efforts will be made to limit the imaging dose when IGRT is used. This can be accomplished by avoiding the use of this technology to make small changes in patient positioning that are within the stated PTV margins. The imaging dose to the patient may become significant if repeated studies are done for patients with severe set up problems (e.g. requiring frequent corrections that are larger than the PTV margins). It is recommended that patients demonstrating severe set up problems during the first week of treatment be moved to a treatment with larger margins.

6.2 Definition of Dose-Limiting Toxicity

Management and dose modifications associated with the above AEs are outlined in Section 7.

DLTs will be captured until 4 weeks after completion of IPdR therapy and will be graded according to the CTCAE v5.0. DLTs will be defined as clinically significant grade 3 or 4 toxicities possibly or probably related to study treatment.

- Grade 4 neutropenia (ANC < 500/mm³)
- Grade 4 electrolyte toxicities
- ANC <1000/mm³ with fever (temp >101 F) or infection
- Grade 4 thrombocytopenia: Platelets <25,000/mm³
- Platelets <50,000/mm³ requiring transfusion
- Grade 3 or 4 treatment related non-hematologic toxicities excluding alopecia.
- Patients who receive <67% of intended IPdR secondary to treatment related toxicities will also be considered as having a DLT

In addition, during chemoradiation, DLTs will also include AEs requiring interruptions of radiation for >5 consecutive scheduled fractions (and / or ≥ 9 total scheduled fractions) or for >10 consecutive scheduled doses of capecitabine (and / or ≥ 19 total scheduled doses of capecitabine). The following AEs will not be considered DLTs:

- Any grade of alopecia,
- Grade 3 arthralgia or myalgia,
- Brief (<1 week) grade 3 fatigue,
- Grade 3 fever,

- Grade 3 diarrhea or vomiting responding to supportive care
 - Grade 3 nausea, vomiting or diarrhea will be considered a DLT if it occurs for greater than 48 hours despite maximal medical support.
- Grade 3 radiation dermatitis,
- Grade 3 or 4 electrolyte abnormalities will not be considered DLTs if the electrolyte disorder can be corrected to grade 2 or less within 72 hours.

All patients who have received at least one dose of IPdR are evaluable for toxicities.

For dose escalation decisions, patients should have completed $\geq 80\%$ of the planned chemoradiation doses unless the reason for discontinuation is an AE that qualifies for DLT.

Dose escalation will proceed within each cohort in Part IB according to the following scheme. DLT is defined above.

Number of Patients with DLT at a Given Dose Level	Escalation Decision Rule
0 out of 3	Enter 3 patients at the next dose level.
≥ 2	Dose escalation will be stopped.
1 out of 3	Enter 3 more patients at this dose level. 
• If 0 of these 3 patients experience DLT, proceed to the next dose level.• If 1 or more of this group suffer DLT (i.e. 2 of 6 patients), then dose escalation is stopped, and this dose is declared the maximally administered dose.
≤ 1 out of 6 at highest dose level below the maximally administered dose	This is generally the recommended phase 2 dose. At least 6 patients must be entered at the recommended phase 2 dose.

During the MTD dose finding portion, patients who are removed from study for reasons other than a DLT will be replaced.

6.3 Dose Expansion Cohorts:

For the expansion cohort, patients will continue to be monitored for occurrence of DLT. Three additional patients will be treated at the dose level below the dose associated with DLT to establish the MTD. The MTD is defined as the dose below which 2 or more of 3 to 6 patients experience DLT. The MTD will be deemed to be RP2D if $\geq 80\%$ of the patients are able to receive $\geq 80\%$ of the planned treatment doses. Monitoring of all safety and toxicity data is done by the Principal Investigator and the Corresponding Organization on a real-time basis as data are entered into Medidata Rave using the Web Reporting Module. All participating sites are expected to notify the Principal Investigator when a DLT has occurred.

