Patients will be assessed 4 weeks following completion of study treatment (Week 10 unless there were delays in therapy). This will be the final assessment for study-related toxicity. Patients will undergo surgical resection 8-12 weeks following completion of chemoRT (IPdR), and study-related response will be assessed at that time.

Regimen Description					
Agent	Premedication; Precautions	Dose	Route	Schedule	Study Length
IPdR	Take on an empty stomach, either 1 hour before or 2 hours after meals.	Dose as appropriate for the assigned dose level.	PO	QD ^A	38 days (6 weeks)
Capecitabine	Take within 30 minutes after a meal (breakfast and dinner).	825 mg/m ² ^C	PO	BID Monday morning through Friday evening on RT days ^{B,C}	
RT		1.8 Gy/fraction/day × 28 doses (50.4 Gy total dose)		5 doses per week until week 5 and 3 doses during Week 6 ^D	

^AOn the days of radiation therapy, the daily dose of IPdR will be administered within 30 min - 2 hours prior to radiation. Patients may take dose at home if the timing allows.

^BCapecitabine will be taken Monday morning through Friday evening each week of RT.

^CDosing will be with 150 mg and 500 mg tablets

^DRT will be given only Monday through Friday

QD – Once Daily, BID – Twice Daily, PO – Oral, RT – Radiation therapy

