6.8 Duration of Follow-Up

Patients will be followed for 4 weeks after completion of study treatment, removal from study, or until death, whichever occurs first. Patients will be assessed at 4 weeks (approximately 30 days) following completion of IPdR (Week 10 unless there were delays in therapy). This will be the final assessment for study-related toxicity. Patients will undergo surgical resection 8-12 weeks following completion of study treatment, and study-related response will be assessed at that time. Patients removed from study for unacceptable AE(s) will be followed until resolution or stabilization of the adverse event.

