7.2.2 Management of IPdR for delay in radiation therapy

IPdR is administered either once daily or twice daily, 7 days a week, beginning with the first dose of capecitabine on Day 1. IPdR must be taken 7 days/week for the duration of radiation therapy (*i.e.* to be discontinued only following the final dose of radiation therapy). If radiation therapy is held, IPdR continues unless criteria for dose adjustment is met per Section 6.2. IPdR either once daily or twice daily, 7 days a week, will continue through the last dose of radiation therapy. Patients may receive up to 5 additional days (10 doses) of IPdR to accommodate delays in radiation therapy.

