7.3 IPdR and Capecitabine treatment management

Capecitabine and IPdR dose modifications are detailed in Table 7 and Table 8.

Additionally, the following dose modification instructions must be followed:

- All dose modifications should be based on the AE requiring the greatest dose modification.
- If RT is not administered (holiday, weekend, RT related toxicity, *etc.*), capecitabine is held; however, IPdR and RT continue per protocol unless otherwise contraindicated.
- If capecitabine and/or IPdR are held or discontinued, RT continues per protocol unless otherwise contraindicated.
- Capecitabine doses that have been reduced may not be escalated.
- IPdR doses that have been reduced may not be escalated.

Table 7: Capecitabine and IPdR dose levels

	Dose Level 0 Starting Dose (mg/m²)	Dose Level -1 (mg/m²)	Dose Level -2 (mg/m²)	Dose Level -3
Capecitabine	825 (BID) on days when RT is given	620 (BID) on days when RT is given	465 (BID) on days when RT is given	Discontinue
	Dose Level 0 Starting Dose	Dose Level -1	Dose Level -2	Dose Level -3

	Dose Level 0 Starting Dose (mg/m²)	Dose Level -1 (mg/m²)	Dose Level -2 (mg/m²)	Dose Level -3
IPdR	Part IA: Assigned dose level Part IB: see Table 6	Decrease one dose level (minimum dose is 75 mg QD; subjects requiring further dose reduction must have IPdR discontinued) See Tables 5 and 6 for Parts IA and IB dose levels	Decrease one dose level (minimum dose is 75 mg QD; subjects requiring further dose reduction must have IPdR discontinued) See Tables 5 and 6 for Parts IA and IB dose levels	Decrease one dose level (minimum dose is 75 mg QD; subjects requiring further dose reduction must have IPdR discontinued) See Tables 5 and 6 for Parts IA and IB dose levels

Table 8: Treatment management for capecitabine and IPdR

Important table instructions:

- Hold capecitabine and IPdR doses until any AE requiring dose modification returns to \leq grade 1 unless indicated otherwise in the treatment management sections/tables. If recovery to \leq grade 1 (or to other level specified) has not occurred after 3 weeks of delay, study therapy must be discontinued.
- All modifications in dose levels apply to both capecitabine and IPdR unless otherwise noted.

CTCAE v5.0 Adverse Event/Grade	Modifications for AEs that REQUIRED DELAY IN TREATMENT

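### The DLT window in 6.2 runs from the end of IPdR, not the end of study treatment, so it closes early for patients whose RT outlasts IPdR

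*Combined protocol and SAP*

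**What the plan says.** Section 6.2 sets the end of the DLT window: "DLTs will be captured until 4 weeks after completion of IPdR therapy". Its next sentence defines the event by the whole combination: "DLTs will be defined as clinically significant grade 3 or 4 toxicities possibly or probably related to study treatment".

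The Schema and Section 6.1.1 use a different clock for the last toxicity visit: "Patients will be assessed 4 weeks following completion of study treatment", given as Week 10 if there are no delays. The study calendar (Section 11) labels the same visit as four weeks after chemoRT. Section 6.8 uses both clocks. Follow-up runs from the end of study treatment, and the next sentence puts the assessment at 4 weeks "following completion of IPdR (Week 10 unless there were delays in therapy".

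Two provisions let IPdR end before RT. Section 7.3 says: "If capecitabine and/or IPdR are held or discontinued, RT continues per protocol unless otherwise contraindicated". Section 7.2.2 has patients continue IPdR to the final fraction, but then adds a limit: "Patients may receive up to 5 additional days (10 doses) of IPdR to accommodate delays in radiation therapy". Section 7.2 has missed fractions made up at the end, with no limit in days, and Section 7.2.1 gives capecitabine on each RT day.

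**The concern.** The endpoint is the toxicity of three concurrent treatments, but the window closes on one of them. When IPdR ends first, the 4-week clock is already running while the patient still receives RT, and often capecitabine. The same event on the same day after the last fraction could then be a DLT in one patient and not in another at the same dose level.

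Cohorts are small, so single events matter. Under the escalation table in 6.2, one uncounted DLT turns 1 of 3 into 0 of 3, or 2 of 6 into 1 of 6, and escalation proceeds where the table would otherwise expand the cohort or stop. Sites also have two possible dates for the last toxicity assessment.

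**Working it through.** **Inputs.** RT is 28 fractions, Monday to Friday, with Day 1 a Monday; the last is on Day 38 (calendar). IPdR is taken daily on Days 1-38 (calendar). IPdR may be extended by 5 days (7.2.2). At least 4 fractions are required per week (7.2). Three rules in 6.2 matter: less than 67% of intended IPdR because of toxicity is a DLT; an AE-driven RT interruption of more than 5 consecutive or at least 9 total fractions is a DLT; and escalation decisions require at least 80% of planned chemoradiation doses.

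**The plan's own figure.** 38 + 28 = Day 66, and 66/7 = 9.4, which falls in Week 10. Both anchors reproduce the stated Week 10, so nothing is lost on schedule.

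**Formula.** Days lost = (last RT day + 28) - (last IPdR day + 28) = last RT day - last IPdR day.

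**(a) IPdR stopped, RT on time to Day 38.**
- 80% of 38 doses is 30.4, so 31 doses are needed. Stop after Day 31: 31/38 = 82%. Capture ends on Day 31 + 28 = 59 instead of 66, 7 days early, with 5 fractions still to come at the stop.
- 67% of 38 is 25.46, so 26 doses are needed. Stop after Day 26: 26/38 = 68%. Capture ends on Day 54, 12 days early, with 8 fractions still to come. This patient enters escalation decisions only if the 80% rule does not count IPdR.
- Both cases assume that every earlier dose was taken. Earlier holds mean a later stop day for the same percentage, and so a smaller gap.

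**(b) RT delayed, IPdR ending by Day 38 + 5 = 43.**

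| Missed fractions | Last RT day | Last IPdR day | Days lost |
|---|---|---|---|
| 0-3 | 38, 39, 40, 43 | same | 0 |
| 4 | 44 | 43 | 1 |
| 5 | 45 | 43 | 2 |
| 6 | 46 | 43 | 3 |
| 7 | 47 | 43 | 4 |
| 8 | 50 | 43 | 7 |

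At the 4-per-week minimum, 28/4 = 7 weeks, so RT ends on Day 46 or 47 and 3-4 days are lost. Eight missed fractions is the largest total below the 9-fraction DLT limit. It already breaks the weekly minimum: RT ends on the Monday of Week 8, leaving 27 fractions in seven weeks, against 4 × 7 = 28.

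The IPdR limit is itself ambiguous under once-daily dosing. If its 10 doses mean ten once-daily days, IPdR can run to Day 48. The loss at eight missed fractions is then 50 - 48 = 2 days, and at seven or fewer it is nil.

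**Which stops are not already DLTs.** From Table 8, read with 6.2 and 7.3:
- a third occurrence of grade 2-3 diarrhea, where each episode was grade 2 or was grade 3 responding to supportive care;
- a required reduction below the 75 mg once-daily minimum;
- a low-grade seizure.

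Each ends IPdR while RT continues. The diarrhea route stops capecitabine as well.

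**Sensitivity, on assumptions that are not in the documents.** For a true DLT rate p and q = 1 - p, the 3+3 probability of escalating is q³ + 3pq² × q³. At p = 0.33 this is 43.4%. Suppose 10-50% of patients are affected and 5-20% of their DLTs fall in the gap. The counted rate is then 0.33 × (1 - 0.10 × 0.05) = 0.328 to 0.33 × (1 - 0.50 × 0.20) = 0.297, and the probability of escalating is 43.8% to 50.0%.

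**The case against.** The strongest reply is that the protocol treats the two anchors as one. The Schema and 6.1.1 bracket IPdR with chemoRT when timing surgery, 7.2.2 has IPdR run to the last fraction, and 9.1 defines the MTD by DLTs attributable to IPdR. That explains the wording, and the anchors do coincide on schedule. It does not settle the off-schedule cases, because 7.3 and the limit in 7.2.2 allow IPdR to end first and 6.2 itself attributes DLTs to study treatment. Reading completion as planned completion would remove the gap in (a), but the text does not say so, and the gap in (b) would remain.

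Second, the DLT rules already cover much of the affected group. Related grade 4 non-hematologic events that end IPdR are generally DLTs. Non-recovery after 3 weeks leaves at most 17/38 = 45% of IPdR, which is a DLT if treatment-related. This stands, and it shrinks the group without emptying it.

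Third, adverse events are still collected: at the Week 10 visit, on the late adverse event form, and as attributable serious events beyond 30 days. This also stands. What is lost is the DLT label and its use in escalation, not the safety record.

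A reader might infer that the shortening falls mostly on patients with toxicity. The documents do not show that. Section 7.2 names holidays, equipment and weather among the causes of RT delay, and the toxicity stops most likely to matter are often DLTs already.

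**Conclusion.** The conflict in the text is real, and its effect is confined to off-schedule patients. Capture closes 7 days early after a Day 31 IPdR stop, and 12 days early after a Day 26 stop if the 80% rule excludes IPdR. With RT delay alone it closes about 3-4 days early at the weekly minimum, and 7 days early at eight missed fractions. These RT-delay figures assume that the 5-day limit is binding and means calendar days.

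When the anchors separate in this way, the rule can only shorten capture, so any effect is toward fewer counted DLTs. It is tempting to conclude that the MTD is biased upward. The documents support that direction as plausible but do not demonstrate it. They give neither the share of patients affected nor the timing of DLTs, and the escalation figures above show only how the result depends on assumed values. The point merits a correction because it bears on the primary endpoint and costs little, not because harm to the dose decision has been shown.

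**What to change.** In 6.2, replace the end of the window with: *until 4 weeks after the last dose of any study treatment (IPdR, capecitabine or RT, whichever is last)*. Use the same anchor in the assessment sentence of 6.8. The calendar already counts from chemoRT and needs no change. State in 6.2 whether the 80% rule counts IPdR. Reconcile the days and doses in the 7.2.2 limit with each other under once-daily dosing, and with that section's instruction to continue IPdR to the last fraction.

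The cost is a short amendment. The visit already exists, and the longer window still closes before surgery at 8-12 weeks. Escalation decisions wait up to about one to two weeks longer for affected patients. If an early IPdR stop and a long RT delay coincide, the wait is longer: a Day 31 stop with eight missed fractions gives 50 - 31 = 19 days. No dose or management rule changes.

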Neutrophil count decreased: Grade 2 (1000- 1199/mm ³), 3, and 4	Hold capecitabine until \geq 1200/mm ³ . If recovery takes: 1 wk – maintain dose; 2-3 wks – \downarrow one dose level
Platelet count decreased: Grades 2, 3	Hold until \geq 75,000/mm ³ . If recovery takes: 1 wk – maintain dose; 2-3 wks – \downarrow one dose level
Grade 4	Hold until \geq 75,000/mm ³ . \downarrow one dose level

Important table instructions:

- Hold capecitabine and IPdR doses until any AE requiring dose modification returns to \leq grade 1 unless indicated otherwise in the treatment management sections/tables. If recovery to \leq grade 1 (or to other level specified) has not occurred after 3 weeks of delay, study therapy must be discontinued.
- All modifications in dose levels apply to both capecitabine and IPdR unless otherwise noted.

CTCAE v5.0 Adverse Event/Grade	Modifications for AEs that REQUIRED DELAY IN TREATMENT
GI : Diarrhea (despite optimal antidiarrheal management) Grades 2, 3	Treatment must be held for grades 2 and 3 diarrhea to avoid severe complications. 1 st occurrence – ↓ one dose level 2 nd occurrence – ↓ one dose level 3 rd occurrence – Discontinue
Grade 4	Discontinue
Mucositis - oral Grade 2	Maintain dose or ↓ capecitabine one dose level
Grade 3	↓ capecitabine one dose level
Grade 4	Discontinue capecitabine
Vomiting (despite antiemetics) Grades 2, 3	Hold and delay until \leq grade 1, then ↓ one dose level
Grade 4	↓ one dose level
Investigations (hepatic): Bilirubin, AST, alk phos Grades 2, 3	Hold until bilirubin returns to the baseline grade and AST and alk phos have returned to \leq grade 1; then ↓ one dose level
Grade 4	Discontinue chemotherapy
Febrile neutropenia: Grade 3	Hold until clinical resolution, then ↓ one dose level
Grade 4	Discontinue chemotherapy
Infection: Grade 2	Maintain dose or ↓ one dose level
Grade 3	↓ one dose level
Grade 4	↓ one dose level or discontinue
Nervous system disorders: Seizure Grades 1, 2, 3, 4	Any event of seizure, regardless of grade or attribution, requires discontinuation of IPdR and discussion with the PI regarding the decision to resume treatment.

Important table instructions:

- Hold capecitabine and IPdR doses until any AE requiring dose modification returns to \leq grade 1 unless indicated otherwise in the treatment management sections/tables. If recovery to \leq grade 1 (or to other level specified) has not occurred after 3 weeks of delay, study therapy must be discontinued.

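### Table 6 contradicts the Section 6.1.1 Part IB dose ladder, and because the 67% DLT rule states no counting unit, the conflict can change a DLT call at 300 mg

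*Combined protocol and SAP*

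**What the plan says.** Section 6.1.1 and the Schema list Part IB levels 1B to 7B as 75, 150, 300, 600, 1200, 1800 and 2400 mg QD. Table 6 in Section 7.1 lists 1B to 4B as 75, 150, 225 and 300 mg QD and refers level 5B back to 6.1.1. Table 7 in Section 7.3 points to Table 6 for the Part IB starting dose and for each one-level reduction. At the 75 mg minimum, "subjects requiring further dose reduction must have IPdR discontinued".

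Table 8 fixes when a reduction is required. For diarrhea despite optimal management, "Treatment must be held for grades 2 and 3 diarrhea to avoid severe complications", and the first occurrence costs one dose level. Grade 2 and 3 vomiting and hepatic events also require a hold and then one level down. The table's instructions add: "All modifications in dose levels apply to both capecitabine and IPdR unless otherwise noted". Section 7.3 also says: "IPdR doses that have been reduced may not be escalated". RT continues while the drugs are held.

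In Section 6.2, patients who receive less than 67% "of intended IPdR secondary to treatment related toxicities will also be considered as having a DLT". That bullet names neither a unit nor a grade. The same section lets dose escalation proceed "in Part IB according to the following scheme. DLT is defined above", so whatever the bullet captures enters the 3+3 count.

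**The concern.** The two ladders disagree on the dose assigned at 3B and 4B and on the dose one level below 300 mg. The second disagreement reaches the primary objective through the 67% bullet: if milligrams are counted, the size of the required step largely decides whether a patient falls below 67%. One DLT among three patients expands a cohort and two stop escalation, so one reclassified patient can change the path to the MTD.

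The missing unit also has a wider effect. On the 6.1.1 ladder one step down halves the dose from 150 to 1200 mg, but removes only a third at 1800 mg and a quarter at 2400 mg. On a milligram count the same event with the same hold then weighs more at the lower levels.

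**Working it through.** **The plan's own figure.** Section 11 gives 38 days of IPdR. With RT Monday to Friday, 25 fractions end on Day 33 and the last 3 fall on Days 36-38, so 38 is reproduced. The threshold is 0.67 × 38 = 25.46 full-dose equivalents.

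**Does capsule rounding explain the conflict?** No. 225 mg is 3 × 75 mg and 300 mg is 4 × 75 mg, so both can be given as they stand.

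**Share of intended milligrams after one event.** Let x be the full-dose days before the event (onset day minus 1), h the days held, and f the reduced dose divided by the assigned dose. Held days are lost because RT continues, and the reduced dose is kept to the end:

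share = [x + f(38 − x − h)] / 38

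- 75 mg: f = 0 (discontinue)
- 150, 300, 600 and 1200 mg on the 6.1.1 ladder: f = 0.5
- 300 mg on Table 6: f = 225/300 = 0.75
- 1800 mg: f = 1200/1800 = 0.667
- 2400 mg: f = 1800/2400 = 0.75

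**Day 8 event (x = 7), 3-day hold, assigned 300 mg**

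- Table 6: (7 + 0.75 × 28)/38 = 28/38 = 73.7%, not a DLT
- 6.1.1 ladder: (7 + 0.5 × 28)/38 = 21/38 = 55.3%, a DLT

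**Latest onset day that gives less than 67% of milligrams**

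| Assigned dose (ladder) | 3-day hold | 5-day hold | 7-day hold |
|---|---|---|---|
| 75 mg | 26 | 26 | 26 |
| 150-1200 mg (6.1.1) | 16 | 18 | 20 |
| 300 mg (Table 6) | never | 3 | 9 |
| 1800 mg (6.1.1) | 7 | 11 | 15 |
| 2400 mg (6.1.1) | never | 3 | 9 |

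At 300 mg the two ladders therefore give opposite answers for onset on Days 1-16 (3-day hold), Days 4-18 (5-day) and Days 10-20 (7-day).

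**Does another criterion settle these cases?** Section 6.2 also makes an interruption of more than 10 "consecutive scheduled doses of capecitabine" a DLT. A 7-day hold covers 5 RT days, or 10 doses, which is not more than 10. Shorter holds interrupt no more than that. For a Grade 2 event with such a hold, the 67% bullet decides alone.

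**The gradient is not a cut-off.** For a Day 8 event with a 7-day hold, the share is (7 + 0.5 × 24)/38 = 50.0% at 150-1200 mg, (7 + 0.667 × 24)/38 = 60.5% at 1800 mg and (7 + 0.75 × 24)/38 = 65.8% at 2400 mg. All are below 67%.

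**Counting scheduled doses instead.** With a reduced dose counted as taken, the Day 8 event with a 3-day hold leaves 35/38 = 92.1% at every level from 150 to 2400 mg, on either ladder. A 7-day hold leaves 31/38 = 81.6%. At 75 mg, stopping on Day 8 leaves 7/38 = 18.4%. The boundary lies between 26/38 = 68.4% and 25/38 = 65.8%, so 13 missed doses is the first count below 67%.

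**The case against.** **The bullet may carry a grade floor.** The 6.2 definition opens with Grade 3 or 4 toxicities, and the Part IB wording in 6.1.1 and 9.1 names only Grades 3 and 4. On that reading a Grade 2 event never reaches the bullet. What would remain is mainly Grade 3 diarrhea or vomiting that triggers a Table 8 reduction but is exempt under "Grade 3 diarrhea or vomiting responding to supportive care", a narrow group because more than 48 hours despite maximal support is a DLT. The bullet's added "also" sense and the separate bullet for Grade 3-4 non-hematologic events favor reading it without a floor, but the text does not settle this.

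**The unit may be doses.** Then the ladder conflict cannot change this DLT call. The parallel evaluability rule in 6.1.1 refers to total dose, which leans toward milligrams without deciding it.

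**The 80% completion rule.** For escalation decisions, 6.2 expects at least 80% of planned chemoradiation doses unless the patient stopped for a DLT-qualifying event. In milligrams, the 73.7% patient misses that for IPdR. Capecitabine, stepped from 825 to 620 mg/m², is at [5 + 20 × (620/825)]/28 = 71.5%. Such a patient may not be a clean non-DLT. This point stands, but a patient left out of the count still differs from a patient counted as a DLT.

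**Which ladder is meant?** Section 9.1 promises more conservative increments in Part IB. Table 6's steps from 150 to 225 mg (50%) and from 225 to 300 mg (33%) fit that better than doubling. Against this, the Schema and 6.1.1 agree on all seven levels, and Table 6 itself defers to 6.1.1 at 5B. The sponsor should confirm.

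**Conclusion.** The contradiction between Table 6 and 6.1.1 is in the text and needs no assumption: 3B is 225 or 300 mg, 4B is 300 or 600 mg, and one level below 300 mg is 225 or 150 mg. That it changes a DLT call (73.7% against 55.3% in the Day 8 example) rests on counting milligrams and, for Grade 2 events, on no grade floor. Section 6.2 fixes neither. It also assumes a single event and a 38-day course.

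Three stronger readings are not supported:

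- A reader might infer that early events count as DLTs at 150-1200 mg and never at 1800-2400 mg. The 60.5% and 65.8% above show otherwise.
- A reader might take Table 6 to send 1200 mg (5B) down to 300 mg (4B). Row 5B points back to 6.1.1, where the next level down is 600 mg, so that step is doubtful.
- A reader might want the chance that a cohort stops escalation for this reason. The plan gives no event rate, onset or hold length, and the 80% rule affects who counts, so no such figure is offered.

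The different outcome at 75 mg is not in itself an error. Treating a toxicity-driven stop at the lowest level as a DLT is a defensible cautious choice.

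**What to change.** 1. Replace Table 6 with the 6.1.1 ladder: 75, 150, 300, 600, 1200, 1800 and 2400 mg QD for 1B to 7B.
2. State in 6.2 that the 67% is counted in scheduled IPdR doses taken. A patient who misses 13 or more of 38 for treatment-related toxicity has a DLT, and a dose reduced under Section 7 counts as taken.
3. Keep toxicity-driven discontinuation at 75 mg as a DLT when fewer than 67% of doses are taken.

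The cost is one corrected table and a short addition to 6.2. No new data are needed, because the diaries record each day's capsules and are already reviewed as patients come off study.

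The downside is that a patient stepped down early is no longer a DLT on milligrams alone. The capecitabine and RT interruption criteria remain, as does the 6.3 requirement that at least 80% of patients receive at least 80% of planned doses before the MTD becomes the RP2D.
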